6.2.2.7.3 Reporting of Adverse Events of Special Interest

AEs of special interest will be reported to safety immediately or within 24 hours of the site becoming aware of the event and recorded as such on the Adverse Events eCRF and Safety Adverse Event Form.

Potential DILI will be reported based on specifications mentioned in [Section 6.2.2.6.3](#).

Each AE of special interest is to be assessed to determine if it meets the criteria for an SAE. If an SAE occurs, expedited reporting will follow local and international regulations, as appropriate, and is further outlined in [Section 6.2.2.7.2](#).

6.2.2.8 Follow Up of Adverse Events

All AEs will be followed up through the safety follow-up visits. All SAEs experienced by a patient, irrespective of the suspected causality, will be monitored until the event has resolved, until any abnormal laboratory values have returned to baseline or stabilized at a level acceptable to the principal Investigator and medical monitor, until there is a satisfactory explanation for the changes observed, or until the patient is lost to follow-up.

See [Section 6.2.2.7.1](#) for details related to follow-up of pregnancy. See [Section 6.2.2.6.3](#) for details related to follow-up of potential DILI. See [Section 6.2.2.6.4](#) for details related to follow-up of malignancy.

6.2.3 Vital Signs

Vital signs (blood pressure, heart rate, and body temperature) will be assessed as specified in the Schedule of Assessments ([Table 1](#) and [Table 4](#)). Vital signs will be assessed on Day 0 at predose and at Day 0, 1 and 2 hours (\pm 15 minutes) postdose, as well as on each of the scheduled visit days during the study (excluding PK-only site visits). Supine BP and heart rate recordings will be made after the patient has been recumbent and at rest \geq 5 minutes. When the timing of these measurements coincides with a blood collection, vital signs should be obtained prior to the time of the blood collection.

6.2.4 12-Lead Electrocardiograms

ECG will be assessed as specified in the Schedule of Assessments ([Table 1](#) and [Table 4](#)). ECG recording will initiate after the patient has been supine for at least 5 minutes. On days of PK blood draws, the ECG will be collected before scheduled PK blood draws, though timing will be such that PK draws are collected on their scheduled times where possible.

The ECG will include all 12 standard leads and a Lead II rhythm strip on the bottom of the tracing. The ECG will be recorded at a paper speed of 25 mm/second. The following ECG parameters will be collected: PR interval, QRS interval, RR interval, QT interval, and QT interval corrected for heart rate using Fridericia's formula (QTcF).

All ECGs must be evaluated by a qualified physician or qualified designee for the presence of abnormalities and will be captured electronically and retained for future evaluation if required, up to the time of the clinical study report (CSR) completion.

6.2.5 Physical Examinations

The full physical examination will be completed at screening and Day 0. It includes an assessment of general appearance and evaluation of head, eyes, ears, nose, mouth, throat, neck, thyroid, lymph nodes, and extremities, and dermatologic, respiratory, cardiovascular, gastrointestinal, musculoskeletal, neurologic, and psychiatric systems.

The targeted (limited) physical examination will be completed at all other visits as indicated in the Schedule of Assessments ([Table 1](#) and [Table 4](#)). It includes evaluation of patient complaints and SLE disease-related issues, and will exclude the genitourinary system.

6.2.6 C-SSRS

The C-SSRS is a low-burden measure of the spectrum of suicidal ideation and behavior that was developed by Columbia University researchers for the National Institute of

Mental Health Treatment of Adolescent Suicide Attempters Study to assess severity and track suicidal events through any treatment. It is a clinical interview providing a summary of both ideation and behavior that can be administered during any evaluation or risk assessment to identify the level and type of suicidality present. The C-SSRS can also be used during treatment to monitor for clinical worsening.⁴³

The C-SSRS evaluation will be performed as specified in the Schedule of Assessments (Table 1 and Table 4). Patients with recent (within the past 12 months) or active suicidal ideation or behavior based on patient responding “yes” to question 3, 4, or 5 is exclusionary at screening will be excluded from the study. Patients with recent or active suicidal ideation or behavior at subsequent study visits will have responses to the C-SSRS reviewed in detail to assess patient risk, and appropriate consultative mental health services will be provided.

6.2.7 Injection Site Reactions

Patients will be monitored for local injection site reactions as specified in the Schedule of Assessments (Table 1 and Table 4). Local injection site reactions will be assessed at 2 hours postdose at baseline, and predose for each injection after baseline. Injection site reactions should be managed according to the standard of care. Injection site reactions, Grades 2 to 5, are to be reported as AEs of special interest (see Section 6.2.2.7.3).

6.2.8 Immunogenicity

The serum samples to measure the presence of ADA will be collected as specified in the Schedule of Assessments (Table 1 and Table 4). Blood samples (4 mL) to provide approximately 1.5 mL of plasma for anti BOS161721 antibody analysis will be collected into appropriately labeled tubes containing K₂EDTA. The presence or absence of ADA will be determined in the serum samples using validated bioanalytical methods. Blood samples for ADA analysis will be collected up to Day 90 from all patients. Subsequent ADA samples will be collected from all patients but only analyzed by a central lab if the patient had a positive ADA on Day 90.

After the first dose, if a patient tests positive in the validated confirmatory ADA assay, a sample from this patient will be further analyzed in the neutralizing antibody (nAb) assay by a central lab.

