3 STUDY PLAN

3.1 Study Design

This is a phase 1b/2 combined, randomized, multicenter, double-blind, placebo-controlled trial to study the clinical efficacy, safety, and PK of SC doses of BOS161721 in adult patients with moderately to severely active SLE. After successfully completing a screening phase, eligible patients will be randomized to a specified dose of BOS161721 or placebo. The dosing schedule will be monthly.

The trial will consist of 2 double-blinded portions: MAD phase 1b and POC phase 2. Patients may receive a total of 7 SC monthly doses of study drug on Days 0, 30, 60, 90, 120, 150, and 180, followed by safety follow-up visits at Days 210, 240, and 270.

SLE disease activity assessment data will be centrally reviewed by medical monitor and sponsor to ensure the scores are clinically meaningful and compliant with specific definition. The scope of responsibility includes, but is not limited to, review and confirmation of "A" and "B" BILAG system organ disease, confirmation of clinical components of the SLEDAI-2K score at screening and during the study, and cross-validation of the instruments used in this study to assess the disease activity. Further details on the content and methods of data reports by the medical monitor and sponsor will be outlined in the Medical Data Review Plan along with the processes and procedures that will be followed.

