	-28 to -1	0	15 (± 3)	30 (± 3)	60 (± 3)	90 (± 3)	120 (± 3)	150 (± 3)	180 (± 3)	187 ^b (± 3)	195 ^b (± 3)	210 (± 3)	240 (± 3)	270 (± 3)
Visit Number	1	2	3	4	5	6	7	8	9	--	--	10	11	12
ADA ^l		X	X	X	X	X			X					X
nAb ^m						X			X					
CCI ██████████		X	X			X			X					X
CCI ██████████		X												
CCI ██████████ ██████████ ██████████	X	X		X	X	X	X	X	X			X ⁿ	X ⁿ	X ⁿ
CRP	X					X								X
Serum pregnancy test (women)	X													
FSH (postmenopausal women)	X													
Urine pregnancy test (women) ^o		X		X	X	X	X	X	X					X
TB test (QuantiFERON [®] -TB Gold In-Tube) ^e	X													
Serology (hepatitis B and C, HIV-1/2 combination)	X													

^l Blood samples for ADA analysis will be collected up to Day 90 from all patients. Subsequent ADA samples will be collected from all patients but only assayed (analyzed) if the patient had a positive ADA on Day 90

^m nAb is collected for all patients, though will only be analyzed by central lab if patient is positive for ADA at Day 90

ⁿ CCI ██████████ will not be analyzed during safety follow-up visits

^o Urine pregnancy test will be collected on WOCBP prior to study drug administration on dosing visits

Table 1. Schedule of Assessments - Phase 2 Proof of Concept (POC)

	Screen ^a	Enroll	Treatment Period Follow-up									Safety Follow-Up		
Days	-28 to -1	0	15 (± 3)	30 (± 3)	60 (± 3)	90 (± 3)	120 (± 3)	150 (± 3)	180 (± 3)	187 ^b (± 3)	195 ^b (± 3)	210 (± 3)	240 (± 3)	270 (± 3)
Visit Number	1	2	3	4	5	6	7	8	9	--	--	10	11	12
Stool sample ^p	X													
Spot urine for protein/creatinine ratio	X	X		X	X	X	X	X	X			X	X	X
Urinalysis	X	X		X	X	X	X	X	X			X	X	X
PK Labs^b														
Predose		X		X	X	X	X	X	X					
Postdose			X							X	X	X	X	X

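### ADA samples from Days 180 and 270 are assayed only in patients positive on Day 90, so antibody that first appears after Day 90 cannot be detected, and the nAb trigger is stated in two conflicting ways

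*Protocol*

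**What the plan says.** All references are to the current protocol, V7.0.

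**ADA.** Section 6.2.8 states "Blood samples for ADA analysis will be collected up to Day 90 from all patients". Later samples are also drawn from everyone, but they are "only analyzed by a central lab if the patient had a positive ADA on Day 90". Table 1 (POC schedule, Section 3.4) says the same in footnote l: "but only assayed (analyzed) if the patient had a positive ADA on Day 90". Footnote k of Table 4 (MAD schedule, Appendix 8) carries the same condition. Both schedules place ADA samples on Days 0, 15, 30, 60, 90, 180 and 270. No other section provides for assaying the later samples of a patient who was negative on Day 90.

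**Dosing and follow-up.** Section 3.1 schedules seven injections, given "on Days 0, 30, 60, 90, 120, 150, and 180". It describes this dosing period as "followed by safety follow-up visits at Days 210, 240, and 270".

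**Role of ADA.** Section 2.1 names immunogenicity in the MAD primary objective and lists ADAs among its endpoints. Section 2.2 lists ADAs as a POC safety endpoint.

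**nAb.** The second paragraph of Section 6.2.8 sets no Day 90 condition once dosing has begun: "if a patient tests positive in the validated confirmatory ADA assay, a sample from this patient will be further analyzed in the neutralizing antibody". Section 5.3 and Table 2 footnote g likewise ask only that the patient be ADA-positive. Table 1 footnote m is narrower: "nAb is collected for all patients, though will only be analyzed by central lab if patient is positive for ADA at Day 90". Table 4 footnote l matches footnote m.

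**The concern.** An antibody response can begin at any point during repeated dosing. The protocol goes on dosing for three months beyond the last visit at which everyone is assayed, and it draws the samples that would show a late response. It then leaves them unassayed in exactly the patients in whom a late response would be new.

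What is at stake is an endpoint that the protocol itself links to harm and to loss of drug. Sections 1.2.5 and 1.2.5.3 name immune complex disease and altered drug levels or activity as possible results of ADA. If a Day 90-negative patient loses exposure or response between Day 90 and the Day 210 primary assessment, ADA cannot be examined as a cause. The same limit applies to the interim review behind the POC dose. Section 3.1.2.1 reports no immunogenicity trends with up to 7 doses given in Cohort 1, but for Day 90-negative patients this rule yields no ADA result beyond Day 90.

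This is a laboratory rule. An analysis plan can label the incidence correctly, but it cannot supply results that were never generated.

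**Working it through.** There is no stated figure to reproduce. The check is a count on each side of Day 90, followed by an illustration.

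**1. Logic of the rule.** First positive after Day 90 means negative on Day 90. The condition for assay therefore fails, and neither the Day 180 nor the Day 270 sample is run. The late-onset count is 0 whatever the true rate.

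**2. What lies beyond Day 90.**
- Doses before Day 90: Days 0, 30, 60 = 3 of 7.
- Doses strictly after Day 90: Days 120, 150, 180 = 3 of 7. Including the Day 90 dose, 4 of 7.
- ADA samples subject to the condition: Days 180 and 270 = 2 of 7.
- Study days after Day 90: 270 − 90 = 180, and 180/270 = 67%.

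**3. Patients positive early and negative on Day 90.** Samples up to Day 90 are assayed in everyone, so a patient positive on Day 15, 30 or 60 is counted as positive. What is lost is persistence, because the two later samples are not run. nAb testing depends on which section is followed: 6.2.8, 5.3 and Table 2 footnote g would test this patient, while Table 1 footnote m and Table 4 footnote l would not.

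**4. What assaying everyone would show.** The protocol gives no late-onset rate, so q below is an assumption. With about 110 × 2/3 ≈ 73 active POC patients, a perfect assay and no missing samples, expected cases = 73q and P(at least one) = 1 − (1 − q)^73.

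| Assumed late-onset rate q | Expected cases | P(at least one seen), all assayed | Under the protocol's rule |
|---|---|---|---|
| 1% | 0.7 | 52% | 0 |
| 3% | 2.2 | 89% | 0 |
| 5% | 3.7 | 98% | 0 |
| 10% | 7.3 | >99.9% | 0 |

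**5. Does drug interference justify the rule?** Section 1.2.2.3 gives a mean half-life h of 80 to 87 days (healthy subjects, doses of 30 mg or more). Day 270 is 90/87 = 1.03 to 90/80 = 1.13 half-lives after the last dose. Add up the monthly doses, each decaying as 0.5^(t/h), with one compartment and absorption ignored. In units of one dose, the levels are:
- Day 90 predose: 1.82 (h = 80), 1.90 (h = 87).
- Day 180 predose: 2.66, 2.82.
- Day 270: 1.68, 1.87.

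Day 270 is thus 63 to 66% of the Day 180 predose level and 92 to 98% of the Day 90 predose level. On this model Day 270 is no worse for interference than Day 90, the visit the protocol relies on, but it is hardly better either. With the interim 44-day estimate in Section 1.2.3, Day 270 would be lower (0.62 against 1.25 at Day 90, or 49%), which gives no more support to the rule. The assay's drug tolerance is not stated.

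**The case against.** The rule is stated consistently in three places and is evidently deliberate. Everyone is assayed at five visits (Days 0, 15, 30, 60 and 90). Clinical events tied to ADA are recorded as adverse events to Day 270. PK sampling also runs to Day 270, at all MAD sites and at selected POC sites, so some loss of exposure would be seen without an ADA result. The primary efficacy analysis does not use ADA. The endpoint is listed simply as ADAs, with no time window. All of this stands. It limits the consequence, but it does not make a late response detectable.

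Some stronger readings are tempting, and the documents do not support them:
- A reader might infer that patients positive on Days 15 to 60 and negative on Day 90 drop out of the count. They do not (working, step 3).
- A reader might treat Day 270 as a washout sample, more informative than the rest. It is only about one half-life after the last dose, with modelled drug levels close to the Day 90 trough at the final half-life estimate.
- A reader might say the late samples are discarded. The protocol leaves them unassayed and does not order their destruction, so later assay remains open.
- A reader might say the trial passes off a Day 90 incidence as an incidence to Day 270. The protocol defines no such incidence, and labelling is properly a matter for the analysis plan.
- A reader might want a figure for the under-count. Any such figure would be an assumed total rate multiplied by an assumed late fraction, and the protocol supplies neither.

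**Conclusion.** The point holds for both study parts: as written, ADA incidence is observable only to Day 90, and antibody first appearing later is counted as zero at any true rate. The error can only lower the count. Its size is unknown. The table in the working shows what full assay could reveal under assumed rates and is not an estimate for this drug.

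The nAb conflict is a plain inconsistency and needs reconciling whatever is decided on ADA.

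The change should be made: the endpoint is a listed one and the samples already exist. It does not threaten the primary efficacy conclusion.

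**What to change.** **ADA.** Amend Section 6.2.8, Table 1 footnote l and Table 4 footnote k so that the Day 180 and Day 270 samples are assayed in all patients, whatever the Day 90 result. The cost is at most 110 × 2 = 220 extra assays in POC. Adding the 30 MAD patients gives 220 + 30 × 2 = 280, in so far as their samples are still available, since that part has finished. These are upper limits, because Day 90-positive patients would be assayed anyway and some patients will not reach the later visits. No new visits or ADA draws are needed. Assaying only active-arm POC samples would take about 73 × 2 = 146, but choosing samples by arm needs someone unblinded, so running them all is simpler.

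**nAb.** State one trigger in Section 5.3, Table 2 footnote g, Section 6.2.8, Table 1 footnote m and Table 4 footnote l: any confirmed ADA positive leads to nAb testing. Table 1 collects nAb samples only on Days 90 and 180, so a patient positive on Day 15, 30, 60 or 270 has no same-day nAb sample. The text should say that testing uses the nAb samples the schedule collects, or residual ADA plasma where volume allows. Section 6.2.8 provides about 1.5 mL per ADA sample, and whether that suffices is for the laboratory to confirm.

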6.3 Efficacy Assessments

All efficacy assessments will be performed at times defined in the Schedule of Assessments (Table 1 and Table 4).

6.3.1 SLEDAI-2K

The SLEDAI-2K is a validated instrument that measures disease activity in SLE patients at the time of the visit and in the previous 30 days. It is a global index and includes 24 clinical and laboratory variables that are weighted by the type of manifestation, but

not by severity. The total score falls between 0 and 105, with higher scores representing increased disease activity. The SLEDAI-2K has been shown to be a valid and reliable disease activity measure in multiple patient groups. A SLEDAI -2K of 6 or more generally represents moderately to severely active disease.⁴⁴

6.3.2 BILAG 2004

The BILAG-2004 index is an organ-specific 97-question assessment based on the principle of the doctor's intent to treat. Only clinical features attributable to SLE disease activity are to be recorded and based on the patient's condition in the last 4 weeks compared with the previous 4 weeks. It will be scored as not present (0), improved (1), the same (2), worse (3), or new (4). Disease activity is graded separately for 9 body systems to 5 different grades (A to E) as follows: A ("Active") is very active disease, B ("Beware") is moderate activity, C ("Contentment") is mild stable disease, D ("Discount") is inactive now but previously active, and E ("Excluded") indicates the organ was never involved.⁴⁴ A shift from BILAG-2004 Grade A or B to a lower grade indicates a clinically relevant change in disease activity as the BILAG-2004 grades mirror the decision points for treatment interventions.

Only Investigators that complete BILAG-2004 training will be allowed to perform the BILAG-2004 assessments. Preferably, the same Investigator should evaluate the patient at each BILAG-2004 assessment from screening to study completion. The Investigator must maintain documentation with descriptive details supporting the BILAG-2004 scoring (e.g., chart, worksheet, clinic notes, and labs) at each visit.

See [Appendix 5](#) for detailed specifications.

6.3.3 PGA of Disease Activity

The PGA is used to assess Investigator's general impression on the patient's overall status of SLE disease activity via visual analogue scale (100 mm) with 0 being "very good, asymptomatic and no limitation of normal activities" with 100 mm being "most severe possible disease ever seen in all SLE patients". PGA worsening is defined as an increase of ≥ 30 mm from baseline.

When scoring the PGA, the assessor should always look back at the score from the previous visit.

6.3.4 Composite Endpoints: SRI-4, SRI-5, SRI-6, and BICLA Response

6.3.4.1 SRI-4 Response

The SRI-4 is a composite index of SLE disease improvement that consists of scores derived from the SLEDAI-2K and the BILAG 2004 Index. Response based on the SRI-4 is defined by:

1) ≥ 4 -point reduction in SLEDAI-2K global score; 2) no new severe disease activity (BILAG A organ score) or more than 1 new moderate organ score (BILAG B); and 3) no

deterioration from baseline in the PGA by ≥ 30 mm. The SRI-4 response in patients with moderate to severe SLE is associated with broad improvements in clinical and patient-reported outcomes.⁴⁵

6.3.4.2 SRI-5 and SRI-6 Response

Like the SRI-4, the SRI-5 and SRI-6 are composite indices of SLE disease improvement that consists of scores derived from the SLEDAI-2K and the BILAG 2004 Index. However, the SRI-5 and SRI-6 are computed with a minimal five-point or six-point improvement in SLEDAI-2K being required, respectively.⁴⁶

6.3.4.3 BICLA Response

The BICLA is a responder index developed to measure response to therapy, and it includes scores from the BILAG, SLEDAI-2K, and PGA. BICLA response is defined as: 1) at least 1 gradation of improvement in baseline BILAG 2004 scores in all body systems with moderate disease activity at entry (e.g., all B [moderate disease] scores falling to C [mild], or D [no activity]); 2) no new BILAG A or more than 1 new BILAG B scores; 3) no worsening of total SLEDAI-2K score from baseline; 4) $\leq 10\%$ deterioration in PGA score; and 5) no treatment failure.⁴⁴ It is driven primarily by the BILAG, and has been used in phase 2 and 3 mAb studies.⁴⁷

For the endpoints of BICLA response at Days 210, 240, and 270, patient scores will be completed and response determined.

6.3.5 CLASI Response

The CLASI is a comprehensive tool for assessment of disease activity and damage in cutaneous lupus, shown to be valid, reliable, and sensitive to changes in disease activity.⁴⁸ Response is defined as 50% improvement from baseline in "A" or "B" scores. This assessment will be applied to all patients who have cutaneous disease activity.

For the secondary efficacy endpoint of CLASI response at Day 210, patient scores on MAD and POC studies will be compared with baseline for 50% improvement.

6.3.6 ACR-28 Joint Count

The ACR-28 joint count will evaluate the number of tender and swollen joints in the shoulder, elbow, wrist, hand, knee joints. Joints of the feet are excluded.

6.4 Other Variables

6.4.1 SLICC/ACR Damage Index

The SLICC/ACR damage index is a validated instrument to assess damage, defined as irreversible impairment, continuously persistent for 6 months (ascertained by clinical assessment), occurring since the onset of lupus, and it is based on a weighted scoring system. This index records damage occurring in patients with SLE regardless of cause,

with demonstrated content, face, criterion, and discriminant validity.⁴⁹ It will be performed on Days 0 and 180.

6.4.2 PROs

Patients should be encouraged to complete the PROs at the clinic at the beginning of the study visit prior to any clinical assessments. A member of the staff should be available if a patient requires further instruction and to review the PRO questionnaires for completeness prior to leaving the clinic. The PROs include the CCI [REDACTED] and the CCI [REDACTED] and will be assessed as specified in the Schedule of Assessments (Table 1 and Table 4).

CCI [REDACTED]
[REDACTED] .50

CCI [REDACTED]
[REDACTED]
[REDACTED]

